For patients who experience Grade 3 or 4 diarrhea, or other non-hematologic toxicities, the topotecan dose can be held up to 3 weeks waiting for toxicity to resolve to < Grade 2. Drug may be resumed at that time at same dose. If toxicity does not resolve in 3 weeks, patient will be taken off study. Patients with Grade 2 diarrhea may need to follow the same dose modification guidelines.

Topotecan should not be re-administered unless the neutrophil count is more than or equal to 1.5 x 10^9 /L, the platelet count is more than or equal to 75 x 10^9 /L, and the hemoglobin level is more than or equal to 9 g/dL (after transfusion if necessary).

Standard oncology practice for the management of neutropenia is either to administer topotecan with other medications (e.g. G-CSF) or to dose reduce to maintain neutrophil counts. Please refer to section 4.1 for protocol guideline regarding G-CSF administration.

3.3.4.2 Pazopanib:

For Pazopanib, two dose reductions are permitted, from 600 to 400 or 200 mg daily or from 400 to 200 mg daily. Further dose reduction is not allowed. Patients may be maintained on the lower dose of pazopanib during protocol if deemed to be deriving benefit from the drug. Doses that are reduced for pazopanib related toxicity will not be re-escalated, even if there is minimal or no toxicity with the reduced dose. Patients whose dose has been reduced for adverse events that are subsequently not felt to be related to pazopanib may have the dose re-escalated after completion of one cycle with toxicities less than or equal to grade 1.

3.3.5 Hematologic Toxicity:

Dose Modifications Based on ANC and Platelet Counts (topotecan):

Version Date: 07/17/2025 Page 22 of 96

ANC (/mL)	P	latelets (/mL)	% of Planned topotecar		
> 1500	and	> 75,000	100%		
< 750	or	< 50,000	hold*		

^{*}Topotecan should be held. Upon recovery to ANC $\geq 1,500/\text{mL}$ and platelets to >75,000/mL, the same dose level will be administered.

3.3.6 Non-hematologic Toxicity:

Dose Modifications Based on **topotecan- or pazopanib**-Related Non-Hematologic Toxicities:

NCI Grade	% of Planned Dose
0-2+	100%+
3*	hold**
4	hold***

+For symptomatic Grade 2 toxicity, the suspect drug dose may be held at the discretion of the investigator until recovery to CTC Grade 0-1, then resume at same dose for topotecan or one dose lower for pazopanib.

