- **Hold suspect drug until recovery to CTC Grade 0-1 (or to within 1 grade of starting values for pre-existing laboratory abnormalities), and then resume at same dose for topotecan or one dose level lower for pazopanib.
- ***Hold suspect drug until recovery to CTC Grade 0-1 (or to within 1 grade of starting values for pre-existing laboratory abnormalities), and then resume at same dose for topotecan or two dose levels lower for pazopanib.

3.3.6.1 Management of other drug related complications:

3.3.6.1.1.1 Management of Hepatic effects:

Cases of hepatic failure (including fatalities) have been reported during the use of pazopanib. In clinical trials with pazopanib, increase in serum transaminases (ALT, AST) and bilirubin were observed. In the majority of the cases, isolated increases in ALT and AST have been reported, without concomitant elevations of alkaline phosphatase or bilirubin. The vast majority (92.5%) of all transaminase elevations of any grade occurred in the first 18 weeks.

Monitor serum liver tests before initiation of treatment with pazopanib and at least once every 4 weeks for at least the first 4 months of treatment, and as clinically indicated. Periodic monitoring should then continue after this time period.

The following guidelines are provided for patients with baseline values of total bilirubin \leq 1.5 X ULN and AST and ALT \leq 2 X ULN.

- Patients with isolated ALT elevations between 3 X ULN and 8 X ULN may be continued on pazopanib with weekly monitoring of liver function until ALT return to Grade 1 (NCI CTCAE) or baseline.
- Patients with ALT of >8 X ULN should have pazopanib interrupted until they return to Grade 1 (NCI CTCAE) or baseline. If the potential benefit for reinitiating pazopanib treatment is considered to outweigh the risk for hepatotoxicity, then reintroduce pazopanib at a reduced dose of 400 mg once daily and measure serum

^{*}Except nausea/vomiting (unless patients are on optimal antiemetic therapy).

Version Date: 07/17/2025 Page 23 of 96

liver tests weekly for 8 weeks. Following reintroduction of pazopanib, if ALT elevations >3 X ULN recur, then pazopanib should be permanently discontinued.

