3.3.6.2 Monitoring and management of hypertension

In clinical studies with pazopanib, events of hypertension including hypertensive crisis have occurred. Hypertension (systolic blood pressure ≥ 150 or diastolic blood pressure ≥ 100 mm Hg) occurs early in the course of treatment (39% of cases occurred by Day 9 and 88% of cases occurred in the first 18 weeks).

Blood pressure should be well controlled prior to initiating pazopanib (see 2.1.2.5)

3.3.6.2.1 BP MONITORING:

- Check BP twice weekly for the first 2 months of therapy, then weekly for 2 months, and then once per month thereafter. On days that the patient is not scheduled for clinic visits, BP can be taken at home, local Pharmacy or local Physician's office.
- BP should be taken preferably in the morning and after resting for at least 5 minutes.
- If BP is ≥140/90, then it should be repeated twice (30 and 60 minutes after the first reading). The lowest of these 3 readings will be the one considered for grading and management purposes.
- If BP measured outside the clinic visits is ≥140/90, the result should be immediately reported to the Research Nurse and/or treating physician to take appropriate action as outlined below.

BP MANAGEMENT BASED ON GRADE (CTCAE 4.02):

Hypertension- Adverse Event Grade

Grade 1 (systolic 120-139, diastolic 80-89)

Management

- no need to modify or add anti BP meds; if the patient is already taking BP meds, reinforce need for compliance.
- continue pazopanib and topotecan at same doses.
- add or increase dose of BP meds (at the discretion of

Grade 2 (systolic BP 140-159 or

Version Date: 07/17/2025

diastolic 90-99)*

Page 24 of 96

the treating physician);

- continue topotecan;
- HOLD pazopanib at the discretion of the treating physician until AE recovers to grade 0-1, then restart same dose.

Grade 3 (systolic \geq 160 or diastolic \geq 100)

- add or increase dose of BP meds (at the discretion of the treating physician);
- continue topotecan;
- HOLD pazopanib until AE recovers to grade 0-1, then restart pazopanib reducing 1 dose level.
- DISCONTINUE pazopanib;
- patient finishes trial participation.

Grade 4 (malignant hypertension; transient or permanent neurologic deficit, hypertensive crisis)

*Note: for elevated BP to be considered grade 2 or 3 the patient should be previously normotensive or should be taking BP medication/s regularly.

3.3.6.2.2 IF THE PATIENT IS NOT COMPLIANT:

- REINFORCE need for strict compliance with current BP medication/s,

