3.3.6.13 Diarrhea

Diarrhea, including severe diarrhea requiring hospitalization, has been reported during treatment with oral topotecan. The incidence of diarrhea has been reported to be greater in patients receiving oral topotecan compared to those receiving topotecan i.v. Additionally, in patients with relapsing small cell lung cancer, greater than 65 years of age, there is substantially higher risk of

Version Date: 07/17/2025 Page 26 of 96

severe diarrhea and subsequent hospitalization than in patients less than 65 years of age. Communication with patients prior to drug administration regarding diarrhea and proactive management of all signs of diarrhea is important. Physicians are advised to follow guidelines that describe the aggressive management of this event. This includes use of anti-diarrheal agents, administration of fluids and electrolytes and interruption or discontinuation of therapy with oral topotecan.

Diarrhea related to oral topotecan can occur at the same time as drug-related neutropenia and its sequelae.

3.3.6.14 At the Start of the Next Treatment Cycle:

A new course of treatment may begin when the ANC is at least 1500/mm³ and the platelet count is at least 75,000/mm³ and any other treatment-related toxicities are less than or equal to grade 1. If after a one-week delay, all treatment related toxicities are less than or equal to grade 1, then proceed with treatment at the dose level dictated by the modifications outlined above. If treatment related toxicities have not resolved to less than or equal to grade 1 after a one-week delay, then treatment will be held again, and the patient will be evaluated weekly. If treatment will be held for 2 weeks for treatment related toxicities, then reduce the pazopanib dose by one dose level beyond that indicated by whether or not the patient had DLT in the prior cycle. If retreatment must be held for more than 2 weeks the investigator should be notified. If a patient develops another DLT at the reduced dose or if they experience a life-threatening toxicity at any time, they will be removed from study.

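### For a life-threatening grade 4 non-hematologic toxicity other than hypertension, the within-cycle rules say resume and 3.3.6.14 says remove; some mandatory pazopanib reductions also fall below the 200 mg floor with no stated action.

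*Combined protocol and SAP*

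**What the plan says.** Section 3.3.3 makes dose changes depend on whether the toxicity arises during a 4-week cycle or when the next cycle is due. Sections 3.3.4 to 3.3.6 give the rules for the first case, and 3.3.6.14 for the second.

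**Within a cycle.**
- 3.3.6, grade 4: hold the suspect drug until recovery, "then resume at same dose for topotecan or two dose levels lower for pazopanib".
- 3.3.6, grade 3: the same hold, "then resume at same dose for topotecan or one dose level lower for pazopanib".
- 3.3.6, symptomatic grade 2: the investigator may choose to hold, "then resume at same dose for topotecan or one dose lower for pazopanib". The table itself allows the full planned dose for grades 0 to 2.
- 3.3.4.1: after grade 3 or 4 non-hematologic toxicity, topotecan may be held for up to 3 weeks and resumed unchanged.
- 3.3.6.2, grade 3 hypertension: "HOLD pazopanib until AE recovers to grade 0-1, then restart pazopanib reducing 1 dose level". Grade 4 hypertension ends pazopanib and trial participation.

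**At the start of the next cycle (3.3.6.14).**
- After a 2-week hold: "then reduce the pazopanib dose by one dose level beyond that indicated by whether or not the patient had DLT in the prior cycle".
- Removal: "If a patient develops another DLT at the reduced dose or if they experience a life-threatening toxicity at any time, they will be removed" from the study.

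**Dose ladder (3.3.4.2).** For pazopanib, "two dose reductions are permitted, from 600 to 400 or 200 mg daily or from 400 to 200 mg daily". Then: "Further dose reduction is not allowed". Nothing says what happens instead.

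Section 8.1.3 defines a life-threatening event as one that puts the patient at immediate risk of death. Section 9 counts patients who drop out for toxicity as failures in the Simon designs.

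**The concern.** A site handling a mid-cycle grade 4 event is sent by 3.3.3 to the within-cycle rules. There it finds an instruction to resume, with no exception for a life-threatening event and no pointer to 3.3.6.14. Followed literally, that instruction re-exposes a patient whom the plan removes: at 200 mg if pazopanib is the suspect drug and the patient was on 600 mg, or at the unchanged 0.25 mg if it is topotecan. The sections on arterial thrombosis, hemorrhage and gastrointestinal perforation (3.3.6.4 to 3.3.6.6) report fatal events but offer only cautions or a benefit-risk judgment. For those events the grade 4 footnote is the only within-cycle dose instruction tied to grade.

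At the floor, a site told to lower a dose that cannot be lowered could stay at 200 mg, stop pazopanib and continue topotecan, or end treatment. The choice affects safety first. It can also affect scoring: a patient who leaves for toxicity before the 3- or 6-month landmark is a failure under Section 9, while one kept on treatment and progression-free is a success.

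**Working it through.** The plan gives no figure on this point to reproduce. The check sets the rules side by side and steps through the dose ladder.

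**Step 1: where resume and remove collide.**
- Grade 4, not life-threatening under 8.1.3 (for example a laboratory value, which the footnote expressly covers): the footnote applies and 3.3.6.14 is silent. No conflict.
- Grade 4 hypertension: 3.3.6.2 ends participation. No conflict.
- Other grade 4 non-hematologic toxicity that is life-threatening: 3.3.6 and 3.3.4.1 say resume, 3.3.6.14 says remove. Conflict.

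**Step 2: the ladder.** Inputs: starting dose 600 mg (3.2.1.1); levels 600, 400 and 200 mg (3.3.4.2); one level down for symptomatic grade 2 and for grade 3, two for grade 4 (3.3.6).

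| Current dose | Symptomatic grade 2 (discretionary hold) | Grade 3 | Grade 4 |
|---|---|---|---|
| 600 mg | 400 | 400 | 200 |
| 400 mg | 200 | 200 | none |
| 200 mg | none | none | none |

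Four cells have no dose. Symptomatic grade 2 at 200 mg is not mandatory, because the investigator may continue at 200 mg. That leaves 4 − 1 = 3 of 9 cells, or 3 of the 6 grade 3 and 4 cells. The grade 3 hypertension row gives the same result at 200 mg.

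**Step 3: add the extra level for a 2-week hold.** Grade 3: 600 to 200; none from 400 or 200. Grade 4: none from any level. The count becomes 2 + 3 = 5 of the 6 grade 3 and 4 cells.

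**Step 4: what 3.3.6.14 already settles.** Everyone starts at 600 mg, so a patient on 400 or 200 mg has been reduced before. Assume, from the usage in Section 9, that a DLT is an attributable toxicity of grade 3 or more. If the earlier reduction was for a DLT, a grade 3 or 4 event at the lower dose is another DLT and the patient is removed. Life-threatening events are removed too. What remains is mainly:
- a first DLT at a dose reduced for symptomatic grade 2 or for a hold (600 to 400 to 200 mg is possible without any DLT), where the event is grade 4 at 400 mg or grade 3 or 4 at 200 mg;
- the 2-week-hold reduction where no repeat DLT is involved, such as a first, non-life-threatening grade 4 event at 600 mg: two levels plus one falls below 200 mg.

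**The case against.** The strongest reply is that the texts fit together as a general rule and an override. The footnote never mentions life-threatening toxicity, 8.1.3 does not equate it with grade 4, and 3.3.6.14 applies its removal rule regardless of timing, whatever its heading says. This stands as the better reading. A reader might infer that the plan orders re-treatment after life-threatening events in general; the documents do not support that. Specific stop rules for combined ALT and bilirubin elevation, nephrotic syndrome, wound dehiscence and interstitial lung disease, besides the one for hypertension, narrow the overlap further. What does not go away is that a site reading an unconditional instruction to resume has no prompt to look at the next-cycle section.

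A reader might also infer that nothing governs the patient at the floor. That is too broad. Section 3.3.6.14 covers repeat DLTs; 3.3.2 limits a pazopanib hold to 3 weeks; and 3.7.1.6 ends therapy for a toxicity delay of more than 21 days. These bound an indefinite hold, but none names the action for a patient who has recovered within that time and has no permitted lower dose. Section 3.3.1 sends dosing questions to the Academic PI or the coordinating center, and 7.3.1 provides a team call every other week. That is case-by-case advice, which helps consistency but is not a rule.

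It is also tempting to say that the undefined DLT makes the 400 to 200 mg step contradict the removal rule. It need not: on the Section 9 usage, the step still serves a first DLT after a reduction for grade 2 or for a hold.

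**Conclusion.** The concern holds in a narrow form. The main point is a resume-or-remove conflict confined to non-hematologic grade 4 events, other than hypertension, that are also life-threatening. It amounts to a missing exception in the within-cycle rules and is worth correcting because the literal reading is the unsafe one. The secondary point is a missing floor action in 3 of 9 dose-by-grade cells and for grade 3 hypertension at 200 mg, with more cells affected once the 2-week-hold reduction is added. Section 3.3.6.14 already resolves the repeat-DLT and life-threatening cases among these.

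The statement of what 3.3.6.14 resolves rests on reading DLT as Section 9 uses it. Cells are not patients: the documents give no event rates under these rules, so no patient count can be derived. A reader might infer a loss of power, because toxicity drop-outs are failures and Group B needs only 1 of 14 and then 2 of 32 successes. One patient could decide a stage there, but nothing in the documents supports a power figure.

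**What to change.** Two additions, in one amendment:

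1. In the grade 4 footnote of 3.3.6 and in 3.3.4.1: *If the toxicity is life-threatening (8.1.3), do not resume either drug; remove the patient per 3.3.6.14.*
2. In the grade 3 and grade 4 footnotes of 3.3.6, the grade 3 hypertension row of 3.3.6.2 and the 2-week-hold rule of 3.3.6.14: *If the required level is below 200 mg, do not resume pazopanib.* The sponsor should state alongside it whether topotecan alone may continue.

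The second sentence should not be attached to the discretionary symptomatic grade 2 hold. Stopping there could end treatment for a patient who is benefiting at 200 mg, which 3.3.4.2 allows to continue, and could score that patient as a failure. No new DLT definition is needed for these changes.

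The cost is wording and one sponsor decision, with no added visits or data. The downside is that a few more patients may stop before the landmark and count as toxicity failures under Section 9.

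### For some pazopanib-related ALT rises the 3.3.6 table and the liver rule disagree on the restart dose with no stated precedence, and the fixed 400 mg fails for patients already reduced

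*Combined protocol and SAP*

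**What the plan says.** All references are to the combined protocol and SAP.

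- **General table (3.3.6, Non-hematologic Toxicity).** It covers toxicity related to either drug. Grade 3: hold until recovery, "then resume at same dose for topotecan or one dose level lower for pazopanib". Grade 4: hold until recovery, then "resume at same dose for topotecan or two dose levels lower for pazopanib". The only printed exception, on the grade 3 row, is "Except nausea/vomiting (unless patients are on optimal antiemetic therapy". The footnotes mention pre-existing laboratory abnormalities, so laboratory toxicity is within the table's reach.
- **Liver rule (3.3.6.1.1.1, repeated in 13.2.11.1).** It applies to patients with baseline bilirubin up to 1.5 x ULN and AST/ALT up to 2 x ULN. Its first provision reads "Patients with isolated ALT elevations between 3 X ULN and 8 X ULN may be continued on pazopanib with weekly monitoring of liver function". Above 8 x ULN pazopanib is interrupted and, if benefit is judged to outweigh the hepatic risk, the instruction is "then reintroduce pazopanib at a reduced dose of 400 mg once daily". After that restart, "if ALT elevations >3 X ULN recur, then pazopanib should be permanently discontinued". ALT above 3 x ULN together with bilirubin above 2 x ULN also means a permanent stop.
- **Dose levels (3.3.4.2).** 600, 400 and 200 mg, with nothing lower. A dose reduced for pazopanib-related toxicity is not raised again.
- **Cycle start (3.3.6.14).** A new cycle needs related toxicity at grade 1 or less. After a two-week hold the instruction is to "reduce the pazopanib dose by one dose level beyond that indicated by whether or not the patient had DLT in the prior cycle". Patients are taken off for "another DLT at the reduced dose or if they experience a life-threatening toxicity at any time, they will be removed from study".

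**The concern.** The two rules address the same event and neither yields to the other in words. Two sites could each follow a printed rule and give different pazopanib doses after the same ALT rise. Section 3.3.6.1.1.1 itself reports fatal hepatic failure with this drug, so the restart dose after a serious liver signal should not depend on which paragraph a site reads. In addition, the fixed 400 mg takes no account of the dose the patient was on when the rise occurred.

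**Working it through.** There is no plan figure to reproduce. The check sets the two rules side by side for each current dose.

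**Inputs.** Dose levels 600/400/200 mg (3.3.4.2); table actions (3.3.6); liver rule (3.3.6.1.1.1); cycle-start and removal rules (3.3.6.14); liver-test schedule (3.4.1.1 and the 3.6 calendar note).

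| Pazopanib-related ALT rise | 3.3.6 table | 3.3.6.1.1.1 | Result |
|---|---|---|---|
| Grade 3, above 8 x ULN, on 600 mg | hold, then 400 mg | interrupt, then 400 mg | agree |
| Grade 4, above 8 x ULN, on 600 mg | hold, then 200 mg | interrupt, then 400 mg | differ |
| Grade 3, above 8 x ULN, on 400 mg | hold, then 200 mg | interrupt, then 400 mg | differ; 400 mg is no reduction |
| Grade 4, above 8 x ULN, on 400 mg | two levels lower does not exist | interrupt, then 400 mg | 400 mg is no reduction |
| Above 8 x ULN, on 200 mg | no lower level after grade 3 or 4 | 400 mg, barred by 3.3.4.2 after a pazopanib-related reduction | neither gives a usable dose |
| Grade 3, isolated, below 8 x ULN, within a cycle | hold, then one level lower | may continue | differ, but a site that holds breaks neither rule |

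**Case (i): grade 4 on 600 mg.** The table cuts the dose by (600 - 200)/600 = 67%, the liver rule by (600 - 400)/600 = 33%. A site that restarts cannot follow both. The case needs four conditions:

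- the event is not life-threatening (otherwise removal, 3.3.6.14);
- bilirubin is not concurrently above 2 x ULN (otherwise permanent stop);
- recovery comes within the three-week hold (3.3.2);
- benefit is judged to outweigh risk.

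The documents do not print the ALT limits for grades 3 and 4. Six assumed pairs of lower limits were tried (3/6, 3/8, 4/15, 5/20, 8/20 and 10/20 x ULN). The rules differ for grade 4 on 600 mg under all six.

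**Case (ii): first rise above 8 x ULN at a reduced dose.** Patients reduced after an earlier DLT leave the study at another DLT. Those restarted after an earlier rise above 8 x ULN stop permanently if ALT exceeds 3 x ULN again. Both groups are outside this case. What remains are patients reduced without a DLT, and the protocol creates them in two ways: a reduction after symptomatic grade 2 toxicity (plus-sign footnote of the 3.3.6 table), and a reduction after a two-week hold at cycle start (3.3.6.14). The reduction on restart is (400 - 400)/400 = 0% from 400 mg; from 200 mg it would be a doubling.

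**Below 8 x ULN.** If grade 3 starts at L, the band where the table holds and the liver rule permits continuing runs from L to 8 x ULN: 3 to 8 if L = 3, 5 to 8 if L = 5, none if L is 8 or more. Timing narrows it further. Liver tests are drawn every two weeks twice, then every four weeks before each cycle. So after the week-2 draw in cycle 1, every scheduled test falls at a cycle start, where 3.3.6.14 delays treatment above grade 1 anyway. The difference can arise only at that week-2 draw or at unscheduled or follow-up tests. Section 3.3.6.14 still takes its dose level from the modifications above it, so the restart-dose question in (i) and (ii) is not removed at cycle start.

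**The case against.** The strongest reply is that the protocol's structure supplies the answer. The liver text sits beneath the general table as an event-specific subsection, and it was adapted to this trial by noting the 600 mg dose. The neighbouring hypertension section (3.3.6.2) departs from the table in the same manner: grade 2 restarts at the same dose where the table's footnote goes one level lower, and grade 4 means discontinuation where the table goes two levels lower. That pattern suggests that event-specific sections override the table. This stands as a plausible reading, but no sentence says so. Even if it is granted, case (ii) remains, because the governing rule would then be the one whose fixed dose does not work. One can answer that the word reduced presupposes a patient on 600 mg, with the table as fallback at 400 mg. That is sensible, but the reader must infer it, and at 200 mg the table has no dose either.

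The reply is also right that the cases are narrow and that safeguards exist: weekly tests, interruption above 8 x ULN, stop and removal rules, a named contact for dosing questions (3.3.1) and a team call every other week (7.3.1). These limit the harm; they do not settle the rule. Section 3.3.3 does not settle it either: it chooses among several toxicities, not between two rules for one. Section 6.1.4 treats a laboratory value as an adverse event only if it causes signs or symptoms or needs therapy. If that governed dosing, fewer rises would reach the table, but it is not stated to do so.

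A reader might infer three stronger points that the documents do not support:

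- *Every grade 3 or 4 ALT rise is in conflict.* It is not: for grade 3 above 8 x ULN on 600 mg both rules give 400 mg.
- *A countable number of patients is affected.* Section 13.2.9 gives ALT above 3 x ULN in 126/895 = 14.1% of patients without statins, which would be 66 x 0.141 = 9.3 patients here. That rate comes from monotherapy studies, and nothing in the documents says what share would reach case (i) or (ii).
- *The primary endpoint is affected.* Nothing in the documents links this dosing difference to PFS6 or PFS3.

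**Conclusion.** The point holds as a minor safety issue in the text as written. In case (i) the two rules give 200 mg and 400 mg for the same event, whichever of the tried grade limits is assumed. In case (ii) the liver rule's restart dose is no reduction at 400 mg, and at 200 mg it is barred when the earlier reduction was pazopanib-related. Both conclusions rest on the printed dose levels and rules. The hold-or-continue difference below 8 x ULN is weaker: it depends on a grade 3 limit that the documents do not print, on a permissive wording, and on tests taken within a cycle. Event-specific precedence is probably intended, but it should be stated. No patient count and no effect on PFS is claimed.

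**What to change.** 1. Add to the 3.3.6 table: *Within a cycle, for patients meeting the baseline limits in 3.3.6.1.1.1, isolated ALT and combined ALT/bilirubin elevations follow 3.3.6.1.1.1; other liver events follow this table; 3.3.6.14 is unchanged.* The baseline limit matters because eligibility (2.1.1.10) admits ALT and AST up to 2.5 x ULN, while the liver rule covers baseline values only up to 2 x ULN.
2. In 3.3.6.1.1.1 replace the fixed restart dose with: *one dose level below the current dose (400 mg from 600 mg, 200 mg from 400 mg); if already at 200 mg, discontinue pazopanib.*

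This settles case (i) at 400 mg. A two-level step for grade 4 would be a clinical preference for which the documents give no evidence. Section 13.2.11.1 is drug-reference text that still speaks of 800 mg, and editing it is optional.

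The cost is a short amendment, with no added visits, tests or patients. The downside is that a few patients restart at 200 mg instead of 400 mg, or stop pazopanib.
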